The study has a planned enrollment of approximately 330 patients (adult men and women) globally. Patients will receive 3600 mg MHAA4549A, 8400 mg, or placebo in 1:1:1 ratio. The number of patients on PPV should not exceed 45% of the total enrolled patients.

Target Population

Inclusion Criteria

Patients must meet the following criteria for study entry:

- Men or women ≥ 18 years of age on day of signing informed consent or obtaining surrogate consent from an authorized representative
- Diagnosis of influenza A where a Sponsor-approved influenza test is used as an aid in diagnosis. A Sponsor-approved influenza test includes:
 - Influenza antigen test –OR–
 - Influenza polymerase chain reaction (PCR) test
- One of the following markers of severity within 24 hours of hospital admission:
 - Requirement for PPV, OR
 - Requirement for O₂ supplementation to maintain SpO₂ > 92% (*Source documentation should show that the patient's SpO₂ was less than 92% off oxygen. Source documentation may consist of either a SpO₂ off oxygen with a value below 92% or a documentation of the Investigator's rationale in lieu of this SpO₂ documentation.*)
- A negative urine or serum pregnancy test for women of childbearing potential
- Patients of reproductive potential must agree to use reliable means of contraception as described below as a minimum (adherence to more stringent local requirements may be required):
 - For women who are not postmenopausal (postmenopausal defined as ≥ 12 months of non-therapy-induced amenorrhea) or surgically sterile (absence of ovaries and/or uterus): agreement to remain abstinent or use two adequate methods of contraception, including at least one method with a failure rate of < 1% per year, during the treatment period and for at least 120 days after the dose of study drug

Abstinence is only acceptable if it is in line with the preferred and usual lifestyle of the patient. Periodic abstinence (e.g., calendar, ovulation, symptothermal, or post-ovulation methods) and withdrawal are not acceptable methods of contraception.

Barrier methods must always be supplemented with the use of a spermicide.

Examples of contraceptive methods with a failure rate of < 1% per year include tubal ligation, male sterilization, hormonal implants, proper use of combined oral or injected hormonal contraceptives, and certain intrauterine devices.

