3. STUDY DESIGN

3.1 DESCRIPTION OF STUDY

3.1.1 Overview of Study Design

This is a Phase 2b (GV29216), randomized, double-blind, placebo-controlled study designed to assess the safety and clinical activity of a single IV dose of 3600 mg MHAA4549A or a single IV dose of 8400 mg MHAA4549A in hospitalized patients with severe influenza A in combination with oseltamivir versus a comparator arm of placebo with oseltamivir. *A Sponsor-approved influenza test that includes influenza antigen test or influenza polymerase chain reaction (PCR) test must be used to diagnose influenza A infection for study eligibility.* This study is planned to take place in approximately 170 study centers globally.

Initially, GV29216 targeted enrollment into two treatment groups: a single IV dose of 3600 mg of MHAA4549A with oseltamivir or a single IV dose of placebo with oseltamivir.

[figure not shown]
In this version of the protocol, patients will be randomized 1:1:1 into three treatment groups: a single IV dose of 3600 mg of MHAA4549A with oseltamivir, a single IV dose of 8400 mg of MHAA4549A with oseltamivir, or a single IV dose of placebo with oseltamivir. *Patients will be stratified by country, PPV versus supplemental O₂ at randomization, and suspected or confirmed bacterial pneumonia versus no bacterial*

pneumonia based on the status at randomization. All patients must begin study drug infusion within 48 hours of hospital admission. In addition, all patients will receive oseltamivir as standard therapy for a minimum of 5 days (10 doses) starting no later than 12 hours after completion of study drug administration. Oseltamivir treatment for longer than 5 days is permitted based on local investigator discretion.

Hospitalized patients with an O₂ or PPV requirement will be evaluated for influenza A infection. Enrollment in this study requires ongoing treatment within 24 hours of hospital admission with one of the following:

- any PPV or
- any supplemental O₂ to maintain oxygen saturation (SpO₂) > 92% ([Section 3.3.2](#))

Patients on PPV should not exceed *approximately* 45% of the total patients enrolled in the study.

[figure not shown]

Safety evaluations will also be provided by an IMC and SOC, as defined in the IMC and SOC agreement (see [Section 3.1.2](#)). If after review of available study data, the IMC and SOC conclude that there is a significant toxicity or worsening disease associated with MHAA4549A, they may recommend stopping further enrollment in the study.

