3.2.2 Rationale for Patient Population and Primary Endpoint

Severe influenza, for the purpose of this study, is defined as requiring one of the following treatments: any supplemental O₂ to maintain an SpO₂ > 92% or PPV. PPV is

defined as any mechanical positive pressure device to maintain oxygenation; this can include positive pressure mask and intubation.

This patient population was chosen based on the rationale that respiratory failure is a hallmark of influenza and a major driver of morbidity and mortality, as well as hospitalization. The recovery from ventilator support has been shown to be directly proportional to time spent in the ICU (Blackwood et al. 2011; Premier Inc, Charlotte, NC). Based upon an analysis of morbidity and mortality, the patient population that requires supplemental O₂ or ventilation on their first day of admission was determined to have a high unmet medical need as they have an estimated mortality of 9%-32%, and 27% require admission to the ICU, according to analysis of a database of over 70,000 hospitalized patients in the U.S. from 2005-2012 (Premier Inc, Charlotte, NC).

The proposed primary efficacy outcome measure in this study is “Time to normalization of respiratory function,” defined as oxygen saturation \geq 95% without oxygen supplementation. Support for use of a respiratory endpoint in this population comes from recently published data demonstrating that a composite endpoint that captured respiratory rate, fever, heart rate, and blood pressure resolution was primarily driven by the respiratory component of the endpoint (Marty et al. 2014). Given that influenza infections generally do not cause systemic infections and influenza disease is restricted to the respiratory tract, the Sponsor believes that the primary endpoint represents a clinically meaningful outcome in this patient population (as shown by analysis of PREMIER database) and measures an important physiologically relevant pharmacodynamic response parameter of MHAA4549A. This endpoint is a measure of patient function, measures a symptom that represents a serious consequence of influenza, and is consistent with clinically relevant endpoints discussed in the US Food and Drug Administration (FDA) Guidance, “Influenza: Developing Drugs for Treatment and/or Prophylaxis” (FDA 2011).

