3.3.3 Secondary Efficacy Outcome Measures

The secondary efficacy outcome measures for this study are as follows:

- *Clinical status of patient at Days 1–7, 14, and 30. This is an ordinal outcome with six mutually exclusive categories:*
 1. *Death;*
 2. *In the ICU;*
 3. *Non-ICU hospitalization, requiring supplemental oxygen;*
 4. *Non-ICU hospitalization, not requiring supplemental oxygen;*
 5. *Not hospitalized, but unable to resume normal activities; or*
 6. *Not hospitalized with full resumption of normal activities*
- Clinical failure after 24 hours post-infusion of study drug; defined as:
 - Progression to increased O₂ requirement defined by an increase in oxygen supplementation from low flow oxygen (i.e., 2–6 L/min) to high flow oxygen

(i.e., >6 L/min) or from oxygen supplementation alone to any PPV or extracorporeal membrane oxygenation (ECMO)

- Progression to ICU
- Prolonged ventilation or O₂ support defined by >2 weeks, or
- Death
- Time to clinical resolution of *abnormal* vital signs (3/5 criteria must be met):
 - SpO₂ ≥ 95% without supplemental O₂
 - Respiratory rate < 24 breaths per minute without supplemental O₂
 - Core temperature < 37.2°C immediately prior to receipt of any antipyretic drug, and at least 6-8 hours from the last dose of antipyretic or core temperature > 36°C in patients who are initially hypothermic
 - Heart rate (HR) < 100 beats/minute
 - Systolic blood pressure (SBP) > 90 mmHg
- All-cause mortality at Day 14, Day 30, and Day 60
- Influenza A viral load in nasopharyngeal samples
 - AUEC (qPCR)
 - Peak viral load (qPCR)
 - *Duration of viral shedding* (qPCR)
- Duration of hospitalization
- Duration of ICU stay
- Antibiotic usage for respiratory infections
- Complications of influenza:
 - Pneumonia (HAP/VAP)
 - Exacerbations of chronic lung disease
 - Myocarditis
 - ARDS
 - Otitis media
 - Other related complications
- All-cause readmission at Day 30 and Day 60
- Duration of ventilation

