6.4 EFFICACY ANALYSES

The primary and secondary efficacy analyses will include all randomized patients who are confirmed to be influenza A infected, with patients grouped according to the treatment assigned at randomization.

Time to event data will be *analyzed* using Kaplan-Meier methodology and stratified Cox proportional hazards models and will be summarized using n, median when estimable, hazard ratios, and 95% confidence intervals. Patients who are lost to follow-up (while event free) will be censored at the time that they are last known to be event free.

The ordinal outcomes will be analyzed using a proportional odds model. To supplement the overall summary odds ratio, separate odds ratios will be estimated for each dichotomized definition of improvement that can be formulated from the components of the ordinal outcome. A test for the proportionality assumption will also be made. Patients discharged from the hospital to a rehabilitation facility will be included in category 5. Patients discharged from the hospital to a nursing home will also be included in category 5, unless the patient lived in a nursing home prior to admission to the hospital, in which case the patient will be characterized based on resumption of normal activities.

Estimation of the treatment difference of proportions and *the corresponding* 95% confidence intervals will be calculated using stratum-adjusted Mantel-Haenszel methodology (Koch et al. 1989). For continuous endpoints, Analysis of Covariance methods (after appropriate transformation of data) will be used to estimate treatment differences and 95% confidence intervals.

Other than censoring in the time to event analyses, no other imputation for missing data will be performed.

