6.4.2 Secondary Efficacy Endpoints

- *Clinical status at Days 1-7, 14, and 30 categorizing proportion of patients in each of the 6 pre-defined categories*
- Proportion of patients with clinical failure after 24 hours post-infusion of study drug
- Median time to clinical resolution of vital signs
- Hazard ratio for mortality at Day 14, Day 30, and Day 60
- Mean and median AUC of viral load

- Mean and median peak viral load
- Median duration of viral shedding in nasopharyngeal samples
- *Proportion of patients with detectable infection*
- Median duration of hospitalization
- Median duration of ICU stay
- Proportion of patients requiring antibiotics for respiratory indications during study
- Proportion of patients with influenza secondary complications
- Median duration of ventilation
- Proportion of patients who are readmitted by Day 30 and Day 60

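### Median ICU stay and median ventilation have no visible rule for never-users or deaths; over all patients the ICU median is probably zero, and among users only the comparison can reverse

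*Combined protocol and SAP*

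**What the plan says.** Section 6.4.2 includes "Median duration of ICU stay" and "Median duration of ventilation" among the secondary efficacy endpoints, without restricting either to patients who used the ICU or a ventilator. Section 6.4 fixes the population: "The primary and secondary efficacy analyses will include all randomized patients who are confirmed to be influenza A infected". That section censors patients lost to follow-up in time-to-event analyses and allows no other imputation. It does not say whether these durations are time-to-event or continuous, whether a patient with no ICU or ventilator time scores zero or drops out, or how a death ends the count.

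Two figures bear on how many patients have any such time. Section 3.2.2 reports, from a US hospital database of patients needing oxygen or ventilation on their first day, that "27% require admission to the ICU". The synopsis says "The number of patients on PPV should not exceed 45% of the total enrolled patients"; section 3.1.1 makes the limit approximate. Section 3.3.3 counts progression to ICU, and progression "from oxygen supplementation alone to any PPV", as components of clinical failure.

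**The concern.** A median describes a duration only when more than half of the patients have one. If most patients never enter ICU and count as zero, the median is zero in every arm whatever the drug does. The obvious repair, dropping patients with no ICU or ventilator time, compares groups formed partly after randomization by events the drug is meant to prevent. A drug that averts short ICU stays leaves the long stays behind and raises the users' median. Under either reading, if death simply ends the stay, an early death gives a short duration and looks like benefit. Two named endpoints could therefore be uninformative or point the wrong way, and the choice between readings would be left to the analyst.

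**Working it through.** The documents give no expected value for either median, so there is no plan figure to reproduce for these endpoints. Table 7 in section 6.1 concerns the primary endpoint. Its first column (71.4%) is matched within a point by a Freedman calculation of pooled active against control, with 330 events, hazard ratio 0.8 and two-sided alpha 0.2: Φ(√(330×2) × 0.2/2.8 − 1.282) = 0.710. Only the 110 patients per arm is carried forward.

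**All patients, never-users scored zero (an assumption; the plan does not state it).** With n = 110, the sample median is exactly 0 when at most 54 patients have any days: P = Bin(54; 110, p), where p is the share with any days. For three arms with equal p, cube it.

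| Share with any days | One arm | All three arms |
|---|---|---|
| 27% | >0.999 | >0.999 |
| 35% | 0.999 | 0.997 |
| 40% | 0.98 | 0.94 |
| 45% | 0.83 | 0.57 |
| 47.75% | 0.65 | 0.27 |
| 50% | 0.46 | 0.10 |
| 50.5% | 0.42 | 0.07 |
| 55% | 0.13 | 0.002 |

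For ICU, the 27% row applies if the trial resembles the database. The conclusion survives a share of about 40%.

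For ventilation, the share that matters is ever ventilated: b + (1 − b)r, where b is the share on PPV at enrolment and r is the rate of later progression to PPV. The documents cap b at about 45% and do not give r. With b = 45%, r = 5% gives 47.75% and r = 10% gives 50.5%. The progression that brings ever-ventilated to one half is (0.5 − b)/(1 − b): 9.1% at b = 45%, 23.1% at 35%, 33.3% at 25%.

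**Users only.** At the same shares this leaves about 0.27 × 110 = 30 ICU patients per arm, and at most about 0.45 × 110 = 50 on PPV at enrolment. To show the direction of the bias, assume 27% ICU in control, half short stays (lognormal, median 3 days) and half long (median 10 days), both with sd(log) 0.5, and a drug that prevents half the short stays.

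- ICU admission: 27% falls to 13.5% + 6.75% = 20.25%.
- Mean ICU days per randomized patient (lognormal mean = median × e^0.125 = median × 1.133): control 0.135 × 3.40 + 0.135 × 11.33 = 1.99; treated 0.0675 × 3.40 + 0.135 × 11.33 = 1.76.
- Median among ICU patients: control √(3 × 10) = 5.5 days. Treated solves (1/3)Φ(ln(x/3)/0.5) + (2/3)Φ(ln(x/10)/0.5) = 0.5, giving x = 7.3 days.
- All-patient median: 0 in both arms.

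Fewer patients enter ICU and fewer ICU days are used, yet the users' median rises by nearly two days and the all-patient median does not move. The sizes rest on the assumed stays; the direction follows from removing short ones.

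**The case against.** Several stronger readings are tempting, and the documents do not support them.

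- *That the trial expects 27% in ICU.* The figure describes a US database and is cited for unmet need. A trial with close to 45% on PPV could have a higher ICU share.
- *That the PPV cap makes the ventilation median zero.* The cap limits PPV at enrolment, not patients ever ventilated. With 45% at enrolment, progression in 9.1% of the rest removes the majority of zeros.
- *That every ventilated subset is affected by treatment.* PPV at randomization is a stratification factor, and section 6.4.3 plans subgroups by those factors. That stratum is a fair comparison for ventilation. ICU has no equivalent, because ICU status at randomization is not a stratification factor, although some ICU entry may precede dosing.
- *That the plan scores never-users zero, or that no rule exists anywhere.* The text is silent, and section 6 defers detail to a separate SAP.

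It is also fair to say that misreading is partly guarded against. The ordinal clinical status covers all patients and ranks death worst and ICU next; clinical failure and mortality are reported separately; and section 6 disclaims formal hypothesis testing. These endpoints would help expose a misleading duration result, but they do not make either median interpretable.

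For hospital stay the zero problem does not arise, since every patient is hospitalized at entry. How far deaths would shorten that median depends on death times the documents do not give, so no size is claimed.

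**Conclusion.** The point stands in a limited form. As written, the two medians have no defined scoring for never-users or deaths. For ICU, if never-users count as zero, the median is 0 with probability above 0.999 per arm at a 27% share and 0.98 at 40%, so it cannot show an effect. For ventilation, zero is likely if few patients progress (0.83 per arm at 45% ever ventilated) and close to a coin toss at one half; a reader should infer instability, not certain zero. Restricting to patients ever in ICU or ever ventilated conditions partly on post-randomization failures and can reverse the direction of effect; patients on PPV at randomization escape this for ventilation. That early death reads as benefit holds if death simply ends the duration, which the plan neither states nor excludes. These are secondary endpoints in an estimation study, so this should be corrected but does not threaten the primary analysis.

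**What to change.** In all confirmed randomized patients, replace the ICU and ventilation medians by ICU-free and ventilator-free days from Day 1 to Day 30. Score death by Day 30 as 0. Score patients who are alive and never in ICU, or never ventilated, as 30, so that they cannot be confused with deaths. Report the stratum-adjusted mean difference with its 95% CI as an estimate, without a test, in keeping with section 6. Keep durations among users as description only, and add ventilation duration in the PPV-at-randomization stratum as a supporting analysis. For hospital stay, keep the endpoint and state how in-hospital deaths are handled, so that death does not count as early discharge.

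The cost is analysis-plan wording: ICU, ventilation and death dates are already needed for the listed endpoints. The drawback is that free days mix death with duration, so mortality and the proportions admitted to ICU and ventilated should be shown beside them.

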6.4.3 Subgroup Analyses

Subgroup analyses will be performed to examine the consistency of the treatment estimates with use of the primary and selected secondary endpoints. Subgroups will include the stratification factors as well as patients who are identified at baseline as influenza A positive by the upper, lower, or both airways and by patients with bacterial co-infections at admission as well as by the influenza season during which the patient was randomized. Additional subgroups may be added following assessment of baseline characteristics as exploratory analyses.

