4.6.2 Diagnostic Testing for Enrollment

All hospitalized patients with severe influenza A must be assessed for disease confirmation prior to and enrollment into the study. A Sponsor-approved influenza test is required as an aid in the diagnosis of influenza A infection. This requires a nasopharyngeal swab be introduced into one nostril. *A lower respiratory tract sample may be used if appropriate for the Sponsor-approved local PCR test.* Note that the influenza antigen test or influenza PCR test result must be available within the 48-hour screening window.

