6. STATISTICAL CONSIDERATIONS AND ANALYSIS PLAN

All efficacy analyses will be conducted according to the intent-to-treat principle and will include all patients who meet the following condition with patients allocated to the treatment arm to which they were randomized:

- Randomized patients who have confirmed influenza A infection as confirmed by a central PCR test from Day 1 samples

Safety analyses will include all patients who were included in the randomization and who received at least one dose of study medication, with patients allocated to the treatment arm associated with the regimen actually received.

No formal hypothesis testing will be done in this study. As a result, no adjustment for a type 1 error will be made to account for the multiplicity of analyses.

Results will be presented both for the MHAA4549A 3600 mg and 8400 mg treatment groups separately and combined for the purpose of comparison to standard of care.

Final efficacy and safety analyses of the total study population will be conducted at the end of the study after all patients have completed all study assessments and the database has been cleaned and closed. Further details of the analyses, including analysis of the exploratory endpoints, will be contained in the statistical analysis plan (SAP) which will be prepared and finalized before the first optional interim analysis (see [Section 6.10](#)) or the final efficacy and safety analysis, if no interim analysis takes place.

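### The nasopharyngeal viral load endpoints have no analysis set of their own, so patients without detectable nasopharyngeal virus at baseline may dilute the estimated effect

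*Combined protocol and SAP*

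**What the plan says.** Section 6 defines a single efficacy population: "Randomized patients who have confirmed influenza A infection as confirmed by a central PCR test from Day 1 samples". It does not say which airway the sample comes from. Section 6.4 applies that population to the secondary endpoints as well: "The primary and secondary efficacy analyses will include all randomized patients who are confirmed to be influenza A infected".

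Section 3.3.3 lists "Influenza A viral load in nasopharyngeal samples" as a secondary outcome, with AUEC, peak and duration of shedding, all by qPCR. Section 6.4.2 summarises these as "Mean and median AUC of viral load", "Mean and median peak viral load" and "Median duration of viral shedding in nasopharyngeal samples". It also adds the proportion of patients with detectable infection, without naming a compartment. For continuous endpoints Section 6.4 prescribes ANCOVA after transformation, names no covariates, and allows no imputation beyond censoring.

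Two places bring in the lower airway. Section 6.4.3 plans subgroups of "patients who are identified at baseline as influenza A positive by the upper, lower, or both airways", as a consistency check on the primary endpoint and on secondary endpoints that it does not list. Section 4.6.2 says of the entry test: "A lower respiratory tract sample may be used if appropriate for the Sponsor-approved local PCR test".

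No readable section limits the nasopharyngeal endpoints to patients with nasopharyngeal virus at baseline, or says how the three measures are scored when the baseline swab is undetectable.

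**The concern.** A nasopharyngeal swab cannot show a fall in virus that was not there. A patient positive only in the lower airway on Day 1 starts with no measurable nasopharyngeal load. If the nose stays negative, that patient has about zero AUEC and peak whatever the treatment, and a shedding duration that is zero or undefined. Never detectable and cleared by treatment then look alike in the data.

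Sections 2.3 and 3.2.4 show what is at stake. Nasopharyngeal viral burden is the stated measure of pharmacodynamic response, and the choice of 3600 mg and 8400 mg rests partly on viral shedding and modelled nasal exposure. If the comparison is attenuated, both the drug effect and the contrast between doses look smaller than they are in patients who had virus to clear. The aim in Section 6.1 is estimation, so a diluted estimate matters even though no test is planned.

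**Working it through.** **Plan's own figure.** There is none to reproduce. Section 6.1 gives power for the primary endpoint only. No SD, effect size or power is stated for viral load, and no share of lower-only patients. All shares below are assumptions.

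**Who can be in the set.** Section 6 requires a positive central Day 1 PCR and names no specimen. Section 6.4.3 lists upper, lower and both. Because both is a separate group, lower means lower only. Lower-only patients can therefore belong to the set unless the central test is run on nasopharyngeal material.

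**Dilution and net gain.** Let f be the share without detectable nasopharyngeal virus at baseline, equal across arms in expectation, and assume they show no effect. Let δ be the mean difference among nasopharyngeal-positive patients.

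- All infected patients: the difference is (1 − f)δ. At equal SD, the enrolment needed for a given precision relative to the effect rises by 1/(1 − f)².
- Restricted set: the difference is δ, but only (1 − f) of patients contribute, so enrolment rises by 1/(1 − f).
- Net advantage of restricting: [1/(1 − f)²] ÷ [1/(1 − f)] = 1/(1 − f).

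| f | Effect retained, all infected | Enrolment factor, all infected | Enrolment factor, restricted | Net advantage |
|---|---|---|---|---|
| 5% | 0.95 | 1.11 | 1.05 | 1.05 |
| 10% | 0.90 | 1.23 | 1.11 | 1.11 |
| 20% | 0.80 | 1.56 | 1.25 | 1.25 |

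**The same comparison as power, for illustration only.** Take 110 per arm (Section 6.1), an assumed two-sided 5% level, and the effect that gives 80% power at f = 0: (1.960 + 0.842) × √(2/110) = 0.378 SD. For f = 5%, 10% and 20%, power is 75.9%, 71.3% and 61.1% with all infected patients, against 78.0%, 75.7% and 70.7% with the restricted set.

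**Medians.** With zeros in a share f of an arm, the arm's median is the (0.5 − f)/(1 − f) quantile of its positive patients: the 47th, 44th and 38th percentiles for f = 5%, 10% and 20%.

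**Two assumptions that move the gain.**

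- *Zeros widen the SD.* If positives have SD 1 and a mean c SDs above zero, the variance in the mixed set is (1 − f) + f(1 − f)c². With c = 2 the SD is √1.26 = 1.12 at f = 10% and √1.44 = 1.20 at f = 20%. All-infected power falls to 61% and 46%. The net advantage, variance/(1 − f), becomes 1.26/0.90 = 1.40 and 1.44/0.80 = 1.80.
- *Day 1 negatives shed later.* If they show a fraction g of the effect, the retained effect is 1 − f(1 − g), and the net advantage at equal SD is (1 − f)/[1 − f(1 − g)]². With g = 0.5 and f = 10% this is 0.90/0.95² = 0.997, so the precision gain disappears.

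**The case against.** The strongest objection is that membership of the efficacy set depends on the central Day 1 PCR, not on the local entry test. A patient enrolled on a lower-tract local PCR still needs central confirmation. If that is done on nasopharyngeal material, lower-only patients are already out. The sampling sections (4.6.5 and 4.6.6) are blacked out, so the readable text cannot settle this. The subgroup wording is also not a product of the Version 7 lower-tract allowance: Section 6.4.3 of Version 5 has the same words, when Section 4.6.2 of that version asked for a nasopharyngeal swab. This stands, and it is why the point is conditional.

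It can also be said that the airway subgroup already supplies the information, and that a separate SAP may define a virology set. The subgroup is a consistency check on endpoints that are not named, so viral load may not be covered. Section 6 does refer to a SAP, but no separate text of it is available here. It may hold a restriction, which cannot be assumed.

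Restriction does not break the randomized comparison. Appendix 1a places Day 1 assessments before study drug unless otherwise indicated, and the plan already selects on a Day 1 PCR.

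A reader might infer more than the documents support:

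- *That lower-only patients certainly are in the analysis.* This is inferred from Section 6.4.3, which does not say how many are expected or which test defines the groups.
- *That the cost is 1.11, 1.23 or 1.56 times the sample size.* Those factors compare the plan with a trial that has no such patients. The restricted set loses the same patients.
- *That the dilution falls on ventilated patients.* No section says who is sampled from the lower tract.
- *That a negative Day 1 swab means no nasopharyngeal virus throughout.* Later shedding is possible.

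**Conclusion.** The point holds in conditional form. One infected set, with no specimen named, serves endpoints measured in the nose, and the plan foresees patients positive only in the lower airway. Unless central confirmation is nasopharyngeal, the nasopharyngeal AUEC, peak and shedding-duration comparisons can include patients with nothing detectable at baseline.

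The consequence is attenuation and lost precision, not bias toward an arm, because the status is fixed before dosing. For assumed shares of 5%, 10% and 20%, the largest attenuation of the mean difference is to 0.95, 0.90 and 0.80, and restricting the set gains about 1.05, 1.11 and 1.25 in efficiency at equal SD. The gain is modest at small shares, larger if zeros widen the SD, and can vanish if Day 1 negatives go on to show about half the effect. A baseline viral load covariate could recover part of the precision, but none is specified.

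**What to change.** In Section 6.4 or the SAP, define the main analysis set for nasopharyngeal AUEC, peak and duration of shedding as randomized, centrally confirmed patients with detectable influenza A in the pre-dose Day 1 nasopharyngeal sample, grouped as randomized. Use the same set for the proportion with detectable infection where that is assessed on nasopharyngeal samples. Keep all infected patients as a sensitivity analysis, and state how each measure is scored there when the baseline swab is undetectable.

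Name the specimen used for the central Day 1 PCR. If it is nasopharyngeal only, saying so closes the point.

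The cost is wording and a slightly smaller n for these endpoints: at 110 per arm, about 105, 99 or 88 patients if the share is 5%, 10% or 20% (110 × 0.95, 0.90, 0.80). The primary endpoint and its population do not change.
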